# 10.8. Appendix 8: IWG Criteria for Response for Participants with MDS

Category	Response Criteria				
Complete Remission	Bone marrow: ≤5% myeloblasts with normal maturation of all cell lines a				
	Persistent dysplasia will be noted a,b				
	Peripheral blood (Response must be maintained for at least 4 weeks)				
	Hgb ≥11 g/dL				
	Platelets ≥100 Gi/L				
	Neutrophils ≥ 1.0 Gi/L b				
	Blasts 0%				
Partial Remission	All CR criteria if abnormal before treatment except:				
	Bone marrow blasts decreased by $\geq$ 50% over pre-treatment but still > 5%				
	Cellularity and morphology not relevant				
Marrow CR b	Bone marrow: $\leq 5\%$ myeloblasts and decrease by $\geq 50\%$ over pre-treatment b				
	Peripheral blood: if HI responses, they will be noted in addition to marrow CR b				
Hematologic	Erythroid (HI-E):				
improvement (HI)	Hgb increase of > 1.5 g/dL				
	decrease of > RBC transfusions/8 weeks versus pretreatment requirement in				
	previous 8 weeks; only RBC transfusions given for a pretreatment Hgb of				
	< 9.0 g/dL count				
	Platelet (HI-P):				
	increase of > 30,000/mL (starting with > 20,000/mL)				
	increase from < 20,000/mL to > 20,000/mL by > 100%				
	Neutrophil (HI-N):				
	increase of > 100% and > 500/µL				
Stable Disease	Failure to achieve at least PR, but no evidence of progression > 8 wks				
Disease Progression	For participants with:				
	
 
Less than 5% BM blasts: ≥ 50% increase in blasts to > 5% blasts
 
				
	
 
5%-<10% BM blasts: ≥ 50% increase to > 10% blasts
 
				
	
 
10%-<20% BM blasts: ≥ 50% increase to > 20% blasts
 
				
	
 
20%-30% BM blasts: ≥ 50% increase to > 30% blasts
 
				
	Any of the following:				
	At least 50% decrement from maximum remission/response in				
	granulocytes or platelets				
	• Reduction in Hab by $\geq 2 \text{ g/dL}$				
	Transfusion dependence				
Non-evaluable	Participant does not meet any of the above criteria				

BM = bone marrow; CR = complete remission; Hgb = hemoglobin; PR = partial remission

d. Dysplastic changes should consider the normal range of dysplastic changes (modification).

e. Modification to IWG response criteria for MDS [Cheson, 2006].

## 10.9. Appendix 9: Response Criteria for Participants with AML

[Modified Cheson, 2003]

**Complete remission (CR):** The subject must achieve a morphologic leukemia-free state ( $\leq 5\%$  blasts) and have no evidence of extramedullary disease. The subject must be free of all symptoms related to leukemia, have an absolute neutrophil count  $\geq 1 \times 10^9$ /L and platelet count  $\geq 100 \times 10^9$ /L, and be transfusion independent.

**CRp:** Marrow response as per CR but platelet count  $<100 \times 10^{9}$ /L.

**CRi:** Marrow response as per CR but platelet count  $<100 \times 10^{9}/L$  or neutrophil count  $<1 \times 10^{9}/L$ .

**Partial remission (PR):** A decrease from baseline of at least 50% in the number of bone marrow blasts, to between 5% and 25% of the bone marrow aspirate.

No response: Subject does not meet criteria for CR, CRp, CRi, or PR.

**Recurrence:** Morphologic relapse, defined as the reappearance of peripheral blasts or increase in bone marrow blasts  $\geq 5\%$  not attributable to any other cause (e.g., infection, growth factor support, bone marrow regeneration).

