Hepatic toxicity	
 
Nonclinical: Hepatic toxicity considered secondary to high cytokine levels was observed after repeat dosing in mice and monkeys (Refer to the IB of GSK3745417).
 
Clinical: No participants have met liver stopping criteria in Study 208850 over the first 3 dose levels. There have been a small
 
	
 
General measures:
 
Inclusion criteria for ALT≤2.5x ULN and bilirubin≤1.5x ULN.
 
Mitigation:
 
Inclusion criteria for ALT ≤2.5x ULN and bilirubin ≤1.5x ULN.
 
Guidelines on the management of potential immune-related AEs is provided in Section 6.4.1.7.
 

		FIOLOCO
Potential Risk of Clinical Significance	Summary of Data/Rationale for Risk	Mitigation Strategy
	number of transient mild ALT and AST elevations though cases are generally confounded by liver metastases.	
 
Standard phase 1 oncology Liver Chemistry Stopping Criteria. (See Section 7.1.5).
 

Hematologic Toxicity	
 
Nonclinical: Nonclinical models showed a transient and dose dependent decrease in red blood cells after dosing.
 
Clinical: Drug-related anemia was observed in Study 208850.
 
AML risks to pancytopenia manifesting as anemia, neutropenia, and thrombocytopenia.
 
	
 
Measures
 
Full supportive care including transfusions are permitted. on study. There are no Hb or platelet inclusion criteria in the protocol as AML patients are generally dependent on regular red blood cell and platelet transfusions. Haemato-oncologists are well experienced in managing hematological toxicity.
 

Reproductive toxicity	No reproductive organ toxicity was observed with GSK3745417 in mice and monkeys. Based on the immune activation mechanism of action, GSK3745417 may affect establishment or maintenance of a pregnancy. There is also a potential risk for embryofetal toxicity.	
 
Mitigation:
 
Exclusion of lactating and pregnant women
 
Contraception guidelines will be included as inclusion criteria for females (Section 5.1).
 
Additional male and female contraceptive requirements if patients are taking a permitted concomitant medication, hydroxyurea, to control blast count (Section 10.5.2).
 

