## 9.4.1. Efficacy Analyses

The safety population will be used for anticancer activity analyses. Since this is a Phase 1 study, anticancer activity will be evaluated based on clinical evidence and response criteria.

Overall response rate (ORR) for AML is defined as the percentage of participants with a complete remission (CR), CRp, CRi, or a partial remission (PR) as per response criteria for AML (Cheson, 2003) and HR MDS (Cheson, 2006), respectively. Participants with unknown or missing response will be included in the denominator when calculating the percentage.

The estimate of ORR along with 95% exact confidence interval (CI) will be provided.

Duration of response (DOR) for AML is defined as the time from first evidence of response to earlier date of disease progression or death due to any cause, for participants with a complete remission (CR), CRp, CRi, or a partial remission (PR) as per response criteria for acute myeloid leukemia. Participants who have not progressed or died at the data cut-off, will be censored at the date of last adequate disease assessment. In addition, participants with an extended time without adequate assessment or who start a new anticancer therapy prior to a DOR event will be censored at the date of last adequate disease assessment (assessment where visit level response is CR, CRp, CRi, or PR) prior to the extended time without adequate assessment or initiation of new anti-cancer therapy, respectively. Further details on rules for censoring will be provided in the Statistical Analysis Plan. DOR will be summarized using Kaplan-Meier quantile estimates along with 95% CIs.

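### Appendix 9 scores one cleared-marrow AML pattern (blasts below 5%, recovered counts, still transfused) as No response, although the same participant with platelets below 100 counts as a responder

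*Protocol*

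**What the plan says.** Protocol Appendix 9 defines four AML response categories and a remainder.

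- **CR:** "The subject must achieve a morphologic leukemia-free state", which the same sentence specifies as at most 5% blasts with no extramedullary disease. The participant must also be free of leukemia symptoms, have neutrophils of at least 1 and platelets of at least 100 (×10⁹/L), "and be transfusion independent".
- **CRp:** "Marrow response as per CR but platelet count" below 100.
- **CRi:** the same marrow condition with platelets below 100 "or neutrophil count" below 1.
- **PR**, which has a blast floor: "A decrease from baseline of at least 50% in the number of bone marrow blasts, to between 5% and 25% of the bone marrow aspirate".
- **The remainder**, labelled No response: "Subject does not meet criteria for CR, CRp, CRi, or PR".

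Transfusion independence appears only under CR. Protocol Section 9.4.1 counts as responders those with "complete remission (CR), CRp, CRi, or a partial remission (PR) as per response criteria for AML" and has no further category. The MDS scale in Appendix 8 does list a marrow CR that does not depend on blood counts; the AML scale has no equivalent.

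Protocol Section 4.1 makes maintenance dosing conditional on CR or PR in both parts. The SAP (Version History and Section 4.8) removes Part 2 after study termination, while SAP Section 4.1.1 still provides for efficacy tables and listings.

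**The concern.** A response scale should not turn a responder into a non-responder because one blood count improves and nothing else changes. Here it does. With a cleared marrow and ongoing transfusions, a rise in platelets from 90 to 110 closes CRp and CRi, and CR stays closed because of the transfusions. The participant drops to the bottom category, below someone whose marrow still holds 24% blasts.

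This matters because ORR is the Part 2 primary efficacy endpoint and is tested against small boundaries: stop at 1 or fewer of 13, and 4 or fewer of 25 (Table 15). The same labels feed any Part 1 response reporting and the CR/PR condition for maintenance.

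**Working it through.** **1. Literal classification.** Inputs are the Appendix 9 conditions above. Counts are ×10⁹/L. No symptoms or extramedullary disease are assumed.

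| Baseline blasts | Blasts now | Neutrophils | Platelets | Transfused | Category |
|---|---|---|---|---|---|
| 60% | 3% | 1.5 | 150 | no | CR |
| 60% | 3% | 1.5 | 150 | **yes** | **No response** |
| 60% | 3% | 1.5 | 90 | yes | CRp/CRi |
| 60% | 3% | 0.8 | 150 | yes | CRi |
| 60% | 24% | 0.2 | 20 | yes | PR (fall 36/60 = 60%) |
| 48% | 24% | 0.2 | 20 | yes | PR (fall 24/48 = 50%) |
| 40% | 24% | 0.2 | 20 | yes | No response (fall 16/40 = 40%) |
| 60% | 5% | 1.5 | 150 | yes | PR if the range includes 5%, otherwise No response |
| 60% | 5% | 1.5 | 150 | no | CR, and also PR if the range includes 5% |

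The rules were also applied to a grid: blasts 0 to 5%, neutrophils 0.5 or 1.5, platelets 50 or 150, transfused or not, baselines 20% to 80%, PR range read as including 5%. The only cleared-marrow combinations scored No response were blasts below 5% with both counts recovered and transfusions continuing. They appeared at every baseline tried.

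**2. Size per participant.** One participant is 1/25 = 4 percentage points of ORR in a full cohort.

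**3. The plan's own design figures (Protocol Section 9.2).** Continue with at least 2 of 13 responders; success with at least 5 of 25.

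- Early stop: (1−p)¹³ + 13p(1−p)¹² = 0.621 at p = 0.10 and 0.064 at p = 0.30.
- Expected N: 13 × 0.621 + 25 × 0.379 = 17.5 under the null; 13 × 0.064 + 25 × 0.936 = 24.2 under the alternative.
- Probability of success: Σ over x = 2 to 13 of P(X = x of 13) × P(at least 5 − x of the remaining 12) = 0.0875 at p = 0.10 and 0.8795 at p = 0.30.

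These match the stated 62.1%, 6.4%, 17.5, 24.2, 0.09 and 0.88.

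**4. Sensitivity.** Let f be the share of true responders who fall in the hole. The documents give no value, so f is an assumption. The counted rate is 0.30 × (1 − f).

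| f (assumed) | Counted rate | Power | Stop at 13 |
|---|---|---|---|
| 0% | 0.300 | 0.879 | 6.4% |
| 10% | 0.270 | 0.809 | 9.7% |
| 20% | 0.240 | 0.711 | 14.4% |
| 30% | 0.210 | 0.585 | 20.8% |

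These figures describe the protocol's Part 2 design, which will not now be run.

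**5. Check of the remedy.** Suppose CRi also covers failure of transfusion independence and PR starts above 5%. The bold row becomes CRi. Both 5% rows get one category each (CRi if transfused, CR if not). Every other row keeps its label.

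**The case against.** **Requiring transfusion independence is a deliberate choice in a modified scale.** That stands for CR. It does not explain the hole: CRp and CRi carry no transfusion condition, so a transfused participant is excluded only when both counts are adequate.

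**The consequence is mostly historical.** This stands. No Part 2 participants will be recruited and no interim analysis will be done. Response is not a visible primary or secondary endpoint of Part 1. Even under the protocol, the futility rules were described as guidance only.

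**The pattern may be rare.** This cannot be answered from the documents. Table 5 says "AML patients are generally dependent on regular red blood cell and platelet transfusions", but it does so to explain the absence of hemoglobin and platelet entry criteria. It says nothing about participants with a cleared marrow and platelets of at least 100. The case is clearest for red-cell transfusion. Where transfusion is holding the platelet count up, one could argue that the true count is below 100, though Appendix 9 does not say so.

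**Stronger readings that a reader might infer, and that the text does not support:**

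- *The whole scale runs backwards.* Only this combination is out of order, and only below 5% blasts. At exactly 5%, an inclusive PR range catches it.
- *Any marrow with 24% blasts is a response.* It needs a fall of at least 50%, hence a baseline of at least 48%.
- *Residual extramedullary disease falls in the same hole.* CR's marrow sentence itself excludes extramedullary disease, so CRp and CRi can be read as excluding it too, and the platelet-driven reversal then disappears. Persisting symptoms with recovered counts do score No response on the literal text, but whether they should count as response is a separate judgement that the documents do not settle.
- *The boundary probabilities measure the bias.* At a true rate of 30%, exactly 2 of 13 has probability 0.139 and exactly 5 of 25 has 0.103. Those are the chances that the count sits on the boundary. A decision changes only if one of those responders is also in the hole.
- *The only way into maintenance or further dosing is lost.* Section 4.1 withdraws only progressive disease after induction and allows additional cycles for stable disease or PR.

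**Conclusion.** The point holds for one cell. As written, a participant with blasts below 5%, no extramedullary disease, no symptoms, recovered neutrophils and platelets, and ongoing transfusions scores No response, while the same participant with lower platelets is a responder. No other rule in the AML response definition catches the case. There is also a small overlap of CR and PR at exactly 5% blasts.

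The effect is one-directional: each affected participant takes 4 points off ORR in a cohort of 25. The total effect is unknown because f is unknown, and the power losses above are conditional on the assumed f. This rests on reading Appendix 9 literally and on treating the case as no worse than CRi, which the scale's own treatment of transfused participants with low counts implies. With Part 2 removed, what is affected now is the protocol's ORR definition and any Part 1 response tables and listings.

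**What to change.** In Appendix 9, for response scoring:

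1. Define CRi as *marrow response as per CR (including no extramedullary disease) without meeting all CR requirements for neutrophils, platelets or transfusion independence*.
2. Give the PR range as *more than 5% and up to 25%*, so that it does not overlap CR.

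Do not remove the PR floor. Doing so would let a cleared marrow with persisting extramedullary leukemia count as PR and would widen the CR/PR condition for maintenance.

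For the terminated study, state the convention in the SAP or study report and flag any Part 1 participant whose label changes.

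The cost is two definitions and slightly more participants counted as responders. Transfusion status would have to come from concomitant-medication records, because the Schedule of Activities has no transfusion row. Appendix 9 also gives no window for judging transfusion independence. After the change that gap separates CR from CRi but no longer moves a participant in or out of ORR.

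The maintenance-entry text in Protocol Section 4.1 names CR and PR but neither CRp nor CRi. It must be reconciled with the revised categories; no clinical rule is proposed here.

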## 10.10. Appendix 10: ECOG Performance Statusa

Grade	Descriptions
0	Normal activity. Fully active, able to carry on all pre-disease performance without restriction.
1	Symptoms, but ambulatory. Restricted in physically strenuous activity, but ambulatory and able to carry out work of a light or sedentary nature ( e.g. , light housework, office work).
2	In bed <50% of the time. Ambulatory and capable of all self-care, but unable to carry out any work activities. Up and about more than 50% of waking hours.
3	In bed >50% of the time. Capable of only limited self-care, confined to bed or chair more than 50% of waking hours.
4	100% bedridden. Completely disabled. Cannot carry on any self-care. Totally confined to bed or chair.
5	Dead.

a. Oken, 1982.

# 10.11. Appendix 11: Cairo-Bishop Clinical Tumor Lysis Syndrome Definition and Grading

	Grade					
Complication	0	1	2	3	4	5
Creatinine ¶∆	≤1.5 x ULN	1.5 x ULN	>1.5-3.0 x ULN	>3.0-6.0 x ULN	>6.0 x ULN	Death
Cardiac arrhythmia ¶	None	Intervention not indicated	Nonurgent medical intervention indicated	Symptomatic and incompletely controlled medically or controlled with device (eg, defibrillator)	Life- threatening (eg, arrhythmia associated with HF, hypotension, syncope, shock)	Death
Seizure	None	-	One brief, generalized seizure; seizure (s) well controlled by anticonvulsants or infrequent focal motor seizures not interfering with ADL	Seizure in which consciousness is altered; poorly controlled seizure disorder; with breakthrough generalized seizures despite medical intervention	Seizure of any kind which are prolonged, repetitive or difficult to control (eg, status epilepticus, intractable epilepsy)	Death

#### Cairo-Bishop clinical tumor lysis syndrome definition\* and grading

ULN: upper limit of normal; HF: heart failure; ADL: activities of daily living.

\* Clinical tumor lysis syndrome defined as laboratory tumor lysis syndrome plus at least one clinical complication.

¶ Not directly or probably attributable to therapeutic agent.

 $\Delta$  If no institutional ULN is specified, age/sex ULN creatinine may be defined as follows: >1 to <12 years of age, both male and female, 61.6 mmol/L; >12 to <16 years, both male and female, 88 mmol/L; >16 years, female 105.6 mmol/L, male 114.4 mmol/L.

Reproduced with permission from: Coiffier B, Altman A, Pui CH, et al. Guidelines for the management of pediatric and adult tumor lysis syndrome: an evidence-based review. J Clin Oncol 2008; 26:2767. Copyright © 2008 American Society of Clinical Oncology. All rights reserved.

ADR	Adverse drug reaction		
AE	Adverse event		
ALT	Alanine aminotransferase		
AML	Acute myeloid leukemia		
AST	Aspartate aminotransferase		
CNS	Central nervous system		
CRP	C-reactive protein		
CRS	Cytokine Release Syndrome		
CV	Cardiovascular		
СҮР	Cytochrome P450		
DMPK	Drug Metabolism and Pharmacokinetics		
DNA	Deoxyribonucleic acid		
ECG	Electrocardiogram		
EU	European Union		
FTIH	First Time in Humans		
GSK	GlaxoSmithKline		
HPLC/MS/MS	High performance liquid chromatography with tandem mass		
	spectrometry		
IB	Investigator's Brochure		
ICH	International Conference on Harmonization		
IFN	Interferon		
IL	Interleukin		
IV	Intravenous		
MABEL	Minimum anticipated biological effect level		
MC	Multicenter		
ND	Not determined		
OATP	Organic anion transporter polypeptide		
OL	Open label		
PD	Pharmacodynamic		
PD-1	Programmed death receptor 1		
PEG	Polyethylene glycol		
P-gp	P-glycoprotein		
РК	Pharmacokinetic		
RP2D	Recommended Phase 2 Dose		
SAE	Serious adverse event		
SD	Standard deviation		
SOC	System organ class		
STING	STimulator of InterferoN Genes		
TBK1	TANK binding kinase-1		
TK	Toxicokinetic		
TNF	Tumor necrosis factor		
Treg	T-regulatory		
WBC	White blood cell		

# CONFIDENTIAL

209809

# **VERSION HISTORY**

SAP Version	Approval Date	Protocol Version (Date) on which SAP is Based	Change	Rationale
SAP	13-JUN-2022	1.0 (25- JAN- 2022)	Not Applicable	Original version
Amendment 1	16-FEB-2024	1.0 (25- JAN- 2022)	Removal of Part 2 analysis and adjustments to Part 1 analysis to algin with study termination	Study termination
Amendment 2	24-FEB-2025	1.0 (25- JAN- 2022)	Correct data error in version history table	Study Closure

# 1. INTRODUCTION

The purpose of this SAP is to describe the planned analyses to be included in the Clinical Study Report (CSR) for Study 209809. Due to the termination of this study, only the planned Part 1 analyses described in the protocol will be produced for a synoptic CSR.

Additional details with regards to data handling conventions and the specification of data displays will be provided in the Output and Specification (OPS) document. Additional data will be available to view via RAPIDO DV (for more details see OPS).

[figure not shown]
# 1.1. Objectives, Estimands and Endpoints

Dose Escalation					
	Objectives	Endpoints			
Primary	To determine the safety, tolerability, and RP2D of a daily dosing schedule (induction) of GSK3745417	Frequency and severity of     Adverse Events (AEs), Serious     Adverse Events, (SAEs), Dose     Limiting Toxicity (DLT),     withdrawals due to AEs			
Secondary	To characterize the pharmacokinetics (PK) of GSK3745417, and relevant metabolites, as applicable, after single and repeat-dose administration.	GSK3745417 concentrations in plasma or PK parameters			
Exploratory					

Dose Escalation		
	Objectives	Endpoints
	CCI	

Estimands will not be considered for this first-time-in-human (FTIH) study.

## 1.2. Study Design

Overview of Stu	udy Design and Key Features
Study intervention	• Part 1 will evaluate a dosing schedule of a 5 days on/2 days off schedule for 2 weeks, and then have an additional 2 weeks off dose for observation for a total of 28 days in each cycle (5 / 2 / 5 q28d). Once an MTD has been established, additional cohorts may be opened to refine dosing frequency optimization. Each cohort will include at least 3 participants. Part 1 will include intra-patient dose escalation for 3 cycles, according to safety and tolerability parameters. The starting dose for Cycle 1 will be escalated in the next dose escalation cohort until a cohort level MTD is reached.
	After 3 induction cycles, if a CR or PR (per appropriate response criteria) is observed, each patient will continue with maintenance weekly dosing at the Cycle 3 dose level until disease progression or unacceptable toxicity. Participants with progressive disease after 3 induction cycles will be withdrawn from study. Participants with stable disease or PR after 3 cycles might receive additional cycles.
Study	This is a FTIH, open-label, non-randomized study.
intervention	
Assignment	

### 2. STATISTICAL HYPOTHESES

With respect to the primary objectives and endpoints of the dose escalation (Part 1), no specific statistical hypotheses are being tested. The primary focus will be on determining the RP2D for induction for further exploration based upon the safety, PK, and anticancer activity profiles of GSK3745417 alone.

# 2.1. Multiplicity Adjustment

Not applicable.

### 3. ANALYSIS SETS

Analysis Set	Definition / Criteria	Analyses Evaluated
Screened	All participants who were screened for eligibility.	Study     Population
Enrolled	All participants who entered the study (who received GSK3745417 or underwent a post-screening procedure). Note: Screening failures (who never passed screening even if rescreened) and participants screened but never enrolled into the study (met eligibility but not needed) are excluded as they did not enter the study.	Study     Population
Safety	All participants who take at least 1 dose of study intervention. Participants will be analysed according to the intervention they actually received.	

Study Population

Safety

Efficacy

DLT-evaluable	
 
All participants who take at least 1 dose of study intervention and are followed for the DLT observation period or are withdrawn within the DLT observation period due to meeting the DLT criteria.
 
Participants unable to receive at least 70% of scheduled doses within the DLT period for other reasons other than toxicity will not be considered evaluable
 
	Safety
PK	All participants from the Safety Analysis Set for whom a PK sample is obtained and analysed.	• PK

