# 4.1.1. Dose Limiting Toxicities (DLT)

All toxicities will be graded using National Cancer Institute – Common Toxicity Criteria for AEs (NCI-CTCAE), version 5.0.

An AE is considered to be a DLT if it is considered by the investigator to be clinically relevant and attributed (definitely, probably, or possibly) to the study intervention and meets at least 1 of the criteria listed in the table below. If an AE is considered related to the underlying disease it is not a DLT. The DLT period is 28 -days starting at Day 1 of each cycle. Participants unable to receive at least 70% of scheduled doses within the DLT

period for reasons other than toxicity (e.g., acute illness, disease progression) will not be considered evaluable.

Toxicity	DLT Definition			
Cytokine Release Syndrome (CRS)	Grade 3 or 4 (See Section 10.4)			
TLS	Grade 3 or Grade 4 TLS (Cairo Bishop criteria, Appendix 11) that cannot be managed/ is not resolved within 72 hours			
Liver Toxicity	ALT $\geq$ 3x upper limit of normal (ULN), plus bilirubin $\geq$ 2x ULN (>35% direct) or plus international normalized ratio (INR)>1.5 (Possible Hy's law)			
Other	
 
Grade ≥3 non-hematologic toxicity of any duration with the following exceptions:
 
Transient (≤ 72 hours) abnormal laboratory value without associated clinically significant signs or symptoms
 
Individual parameters of CRS which collectively constitute <grade 3="" crs<="" li=""> 
Nausea, vomiting, or diarrhea that improves with supportive care within 72 hours
 
Alopecia of any grade
 
Grade 3 fatigue with duration <7 days
 
Grade 3 headache that resolves with supportive treatment to ≤Grade 2 within 24 hours
 
G3 acute renal injury considered related to TLS which improves or resolves with appropriate fluids and management of TLS
 
Grade ≥3 immune-related toxicity that does not resolve to Grade ≤1 or baseline within 8 days despite adequate immune suppressive therapy. Any other event which in the judgment of the investigator and GSK Medical Monitor is considered to be a DLT.
 </grade>

			

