### Table 7Dose-Limiting Toxicities

Participants who withdraw from the study before completing DLT period for reasons other than DLT may be replaced. If a participant experiences a DLT during the DLT period of treatment, the participant will be discontinued from study treatment unless the investigator considers it in the best interest of the participant to continue on study (e.g., in case of symptomatic disease improvement, and/or if the DLT is viewed as preventable in subsequent doses/visits, etc.) and the sponsor approves of the decision.

Guidance for the management of toxicity, including dose modification algorithms, is provided in Section 6.4.

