## 9.3. Analysis Sets

Population	Description	Analyses Evaluated
All screened	All participants who sign the ICF to participate in the clinical study. Participants in this population will be used for the screen failure summary.	Study Population
Safety	All participants who take at least 1 dose of study intervention. Participants will be analyzed according to the intervention they actually received.	Study Population, Safety, Efficacy
DLT-evaluable	All participants who take at least 1 dose of study intervention and are followed for the DLT observation period or are withdrawn within the DLT observation period due to meeting the DLT criteria.	Summary/Listing of Dose-Limiting Toxicities during the Determinative Period
PK population	All participants from the safety population for whom a PK sample is obtained and analyzed.	РК
PD population	All participants who contribute a predose and at least one on-treatment PD/biomarker sample(s).	PD

For purposes of analysis, the following populations are defined:

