## 9.4.2.2. Adverse Events

AEs will be coded using the standard MedDRA and grouped by system organ class. AEs will be graded by the investigator according to the NCI-CTCAE (version 5.0). Events will be summarized with frequency and percentage by preferred term. Separate summaries will be provided for all AEs regardless of grade, treatment-related AEs, treatment-related AEs by maximum grade, serious adverse events (SAEs), treatment-related SAEs, AEs leading to discontinuation of study intervention, AEs leading to dose reductions and AEs leading to dose interruptions/delays. Details will be provided in the statistical analysis plan (SAP). Dose-limiting toxicities (DLTs) will be listed and summarized by dose cohort based on the DLT Evaluable Population. Any AEs

of special interest will be summarized as detailed in the SAP. The incidence of deaths and the primary cause of death will be summarized.

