### 4. STATISTICAL ANALYSES

### 4.1. General Considerations

### 4.1.1. General Methodology

The Safety Analysis Set will be used for all study population, efficacy, and safety analyses, unless otherwise specified. AE and PK related tables, listings and figures will be summarized by dose level. Study population and efficacy tables and listings will be summarized by treatment sequence.

The DLT-evaluable Analysis Set will be used for assessment of dose-limiting toxicities.

Confidence intervals will use 95% confidence levels unless otherwise specified.

Unless otherwise specified, continuous data will be summarized using descriptive statistics: n, mean, standard deviation (std), median, minimum, and maximum. Categorical data will be summarized as the number and percentage of participants in each category.

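### No rule makes every participant with a DLT DLT-evaluable, so non-toxicity missed doses or an unrelated early exit can remove a DLT from the per-cohort summary

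*SAP*

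**What the plan says.** SAP Section 3 gives two routes into the DLT-evaluable set. After at least one dose, participants qualify if they "are followed for the DLT observation period or are withdrawn within the DLT observation period due to meeting the DLT criteria". It then adds: "Participants unable to receive at least 70% of scheduled doses within the DLT period for other reasons other than toxicity will not be considered evaluable".

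Both parts come from the protocol. Protocol 9.3 has the same two routes; its second is for those who "are withdrawn within the DLT observation period due to meeting the DLT criteria". Protocol 4.1.1 supplies the dose rule: those short of 70% "for reasons other than toxicity (e.g., acute illness, disease progression) will not be considered evaluable".

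Protocol 4.1.1 (text with Table 7) also covers what follows a DLT. Treatment stops "unless the investigator considers it in the best interest of the participant to continue on study" and the sponsor approves. On replacement it says: "Participants who withdraw from the study before completing DLT period for reasons other than DLT may be replaced".

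This set drives the DLT outputs. Under Protocol 9.4.2.2, DLTs "will be listed and summarized by dose cohort based on the DLT Evaluable Population". SAP 4.1.1 says: "The DLT-evaluable Analysis Set will be used for assessment of dose-limiting toxicities". SAP 4.2.2 plans a count of patients with DLTs in each cohort.

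**The concern.** An evaluability rule normally serves to remove participants who had too little exposure or follow-up to show that a dose was tolerated. A participant who has already had a DLT has given the answer, and is usually kept whatever happens next. Here evaluability depends on why doses were missed or why the participant left, not on whether a DLT occurred. A DLT followed or preceded by an unrelated problem can therefore fall outside the set.

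DLT frequency is among the Part 1 primary endpoints. The gap works in one direction: it can take a DLT out of the count but cannot add one.

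**Working it through.** The plan states no figure that depends on this wording, so there is none to reproduce. The check is the dose arithmetic, then a case-by-case reading.

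**Dose threshold.** Table 6 of Protocol 4.1 schedules dosing on Days 1–5 and 8–12, so 5 + 5 = 10 doses per cycle.

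- 70% × 10 = 7 doses.
- On schedule, the seventh dose falls on Day 9 (five doses on Days 1–5, the sixth on Day 8, the seventh on Day 9). After that the 70% rule cannot exclude anyone.
- Missing Days 8–10 leaves 5 + 2 = 7 doses, 7/10 = 70%: not excluded.
- Missing Days 8–11 leaves 5 + 1 = 6 doses, 6/10 = 60%: excluded if the reason is not toxicity.

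**Outcome for a participant who has a DLT in the period**

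| Course | Met by | In the DLT count? |
|---|---|---|
| Withdrawn because of the DLT | second entry route | Yes |
| Followed to Day 28, at least 7 doses | first entry route | Yes |
| Followed to Day 28, under 7 doses because of toxicity | first route; dose rule does not apply | Yes |
| Followed to Day 28, under 7 doses for a non-toxicity reason | removed by the 70% rule | **No** (case 1) |
| Continues after the DLT, then dies or leaves the study for another reason before Day 28 | neither route, read literally | **No** (case 2) |

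Case 1 can run in either order because the rule has no time order. A participant may have an early DLT, be allowed to continue, and then miss four or more doses through acute illness. Or a participant may miss Days 8–11 through acute illness, be dosed on Day 12 and have a DLT on Day 13.

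Case 2 depends on how the entry wording is read. Neither document says whether a participant who dies counts as followed, or as withdrawn.

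**Effect on the count.** Removing one participant with a DLT takes one from the numerator and one from the denominator. With the minimum cohort of 3:

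- Counted: 1 of 3.
- Excluded: (1 − 1) of (3 − 1) = 0 of 2.
- Excluded under case 2 and replaced by a participant without a DLT: 0 of 3. The replacement clause depends on the reason for withdrawal and does not ask whether a DLT came first.

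The SAP plans a count and no interval for a DLT rate, so the count is the relevant measure.

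**The case against.** The strongest reply is that the dose rule already protects DLTs. A reader might infer that a participant whose doses are held because of a DLT is excluded. That is wrong: both documents exclude only for reasons other than toxicity. This removes the most likely route to loss, but the exception covers the cause of the missed doses, not the occurrence of a DLT.

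What is left needs an unusual sequence. Stopping treatment is the default after a DLT, and continuing needs the investigator's judgement and sponsor approval. Participants are in hospital throughout dosing, so four doses missed for an unrelated reason should be uncommon. Under Protocol 7, a participant who permanently stops treatment stays in the study, so stopping treatment alone does not create case 2. All of this stands, and it makes the gap narrow without closing it.

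Any such case should also be traceable. AE analyses use the Safety set (SAP 4.2.1), all AEs are listed with subject IDs (SAP 4.2.2), and participants excluded from any population are listed (SAP 6.1.1). This stands too, but the reader has to connect those outputs to find a DLT absent from the DLT table.

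A reader might further infer that an escalation decision or the MTD was distorted. The documents do not support that. Nothing says that this analysis set supplies the data for the N-CRM, and Protocol 4.1.2 has the escalation review cover all AEs, including those that are not DLTs.

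Finally, Part 1 recruitment has finished (SAP 4.8) and the latest SAP amendment gives study closure as its reason. Redefining a primary-endpoint set this late in an open-label study is open to challenge. Here the change can only add participants who had a DLT, so it cannot flatter the drug, but it should be documented as late.

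**Conclusion.** The point holds in a narrow form and is minor. SAP Section 3, like Protocol 9.3 read with 4.1.1, has no rule that a participant with a DLT is always DLT-evaluable, and two describable courses leave a DLT out of the per-cohort summary. Case 1 follows from the wording as it stands. Case 2 assumes a literal reading of the two entry routes.

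The error can only lower the DLT count; one exclusion in a cohort of three turns 1 of 3 into 0 of 2. How often either case would arise is unknown, and no participant is shown to be affected. The events remain in the Safety-set AE outputs. With Part 2 cancelled, the exposure is one descriptive table in the synoptic CSR, although it reports a primary endpoint.

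**What to change.** **Definition.** In SAP Section 3, define DLT-evaluable as at least one dose and either:

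- (a) a DLT within the DLT period, regardless of doses received or the later reason for leaving; or
- (b) followed for the DLT period and not below 70% of scheduled doses for reasons other than toxicity.

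**Cross-check.** Compare the listing of subjects excluded from any population (SAP 6.1.1) with the AE listing and the DLT records, and report any excluded participant who had a DLT. If the DLT table has already been produced, do this as a documented check or a footnote.

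**Separate reconciliation.** The DLT period starts at Cycle 1 in Protocol 1.1 and 4.1 but at each cycle in Protocol 4.1.1 and SAP 4.2.1. These passages must be reconciled. Whichever period is adopted, later-cycle DLTs should still be shown, by the dose received, so that settling the period does not itself drop DLTs from the report.

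**Cost.** One sentence in SAP Section 3 and a comparison of listings already planned, for about 22 participants (the planned Part 1 number; the documents do not give actual enrolment). The period wording needs one further agreed sentence and a place to show later-cycle DLTs.
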